6.7 Sample Size Determination

In the study populations, the actual response rates to receiving the Janssen Ad26.CoV2.S vaccine is not known.

We base our statistical calculations on what is suggested by the existing small, non-randomized reports in the current literature. For example, Kamar et al reported that 26/59 (44%) seronegative patients after two doses became seropositive after a third dose [8]. However, it appears that 17 of the 26 still had anti-S antibody titers <200. Thus, the response rate given the endpoint that we plan for this study (≥ 250 U/ml) would be 9/44 (20%) for those with no antibodies prior to receiving the Janssen Ad26.COVID-19 vaccine and 60% for those with low, but non-zero, levels of antibody prior to receiving the Janssen Ad26.COVID-19 vaccine.

The primary endpoint for our study is a measured anti-S antibody level of ≥ 250 U/ml. Power calculations are based on the comparison at the end of Trial Segment I using a two-sample, two-tailed test of the difference in two proportions. This focuses on whether or not there is a statistically significant difference in the proportion of responders between those patients who had zero antibodies at the time of receiving the Janssen Ad26.COVID-19 vaccine with an adjustment in immunosuppression (N = 150) and those without an adjustment in immunosuppression (N = 150). Effect sizes are based on the square-root arcsine transformation.

Trial Segment I

These power calculations pertain to the randomized arm of **Segment I involving immunosuppression adjustment**: kidney transplant recipients with anti-SARS-CoV-2 spike protein antibody levels = 0 at baseline (i.e. after receiving 2 or more doses of mRNA vaccine) who are randomized to be maintained on their current immunosuppression vs transient immunosuppression adjustment around the time of receiving the Janssen Ad26.CoV2.S vaccine (n=150/arm).

We have performed power calculations using several different assumptions regarding the expected outcomes table below. For example, if we expect that the true response rate of 20% of patients without anti-S antibodies at baseline without an adjustment to their immunosuppression will achieve the primary endpoint after receiving the Janssen Ad26.COVID-19 vaccine, then a true response rate of 37% in the patients in the altered immunosuppression group will reject the null hypothesis of an equal response rate with 90% power. Thus, 120 patients will still have low levels (< 250 U/ml) and 30 will have high levels (≥ 250 U/ml). Of the 100 with low levels prior to receiving the Janssen Ad26.COVID-19 vaccine, we expect that >90 will develop high levels.

Response rate in arm with no alteration in immunosuppression	Response rate in arm with alteration in immunosuppression	Power	Significance level (alpha)
20%	60%	1.00	0.05

10%	24%	0.9	0.05
20%	37%	0.9	0.05
30%	48%	0.9	0.05
23%	40%	0.9	0.05
32%	50%	0.9	0.05
41%	60%	0.9	0.05
52%	70%	0.9	0.05
63%	80%	0.9	0.05

Because we expect a true response rate of 20% and 60% in the patients without and with immunosuppression alteration, respectively, we acknowledge that this study is over-powered for the current enrollment targets. If these were the true response rates, 30 patients would be required for each arm to achieve 90% power. Therefore, even if there is drop out and/or misestimation of the response rates within each category then this study will be sufficiently powered for this comparison.

All tests will be carried out using two-side hypothesis tests with a significance level of 0.05 unless otherwise noted.

For **our other primary objective** (any effective response to the Janssen Ad26.CoV2.S vaccine in kidney transplant patients who had no anti-SARS-CoV-2 spike protein antibodies (<250 U/ml, but >0 U/mL) after 2 or more doses of mRNA vaccine), even a small response rate (1-2%) would be statistically significant. Power calculations pertaining to this endpoint are irrelevant (a very few number of subject will suffice). We also considered an unvaccinated control group for this arm, but in the current environment of COVID infection in the US, we decided that not offering a vaccine to patients who have already failed mRNA vaccination would be unethical. For this non-responder population receiving an additional dose of the Janssen Ad26.CoV2.S vaccine, we would consider a response rate of 20% in the group maintained on their current immunosuppression to be clinically significant. Importantly, patients in Segment I who do not respond to receiving the Janssen Ad26.COV2.s vaccine when maintained on their current immunosuppression will be offered immunosuppression adjustment (Segment II) and receive a second dose of the Janssen Ad26.CoV2.S vaccine.

We expect that response rate of a heterologous additional dose with the Janssen Ad26.COV2.s vaccine of low responders (anti-SARS-CoV-2 spike protein levels at baseline >0 but <250 U/ml) will be high. We would consider a response rate of >50% to be clinically meaningful. The heterologous additional dose with the Janssen Ad26.COV2.s vaccine of low responders was included in this protocol to allow develop data regarding a treatment option for this population of patients. Again, we considered a control group without vaccination in this population, but rejected it considering the high rates of COVID infection currently in the US.

Trial Segment II

The rate of response in prior non-responder to the heterologous additional dose with the Janssen Ad26.COv2.s vaccine who are then managed with a 4th vaccine with reduced immunosuppression is unknown. If we assume the true response rate is 60%, then of the 100 subjects in this study, on average, 60 will have high levels and 40 will have undetectable to low levels.

No data regarding the durability of the anti-SARS-CoV-2 spike protein antibody response is available from the current literature. Thus, power calculations regarding this endpoint were not developed.

6.8 Statistical Methods

In general, univariate descriptive statistics will be calculated, as appropriate for all variables including baseline values for demographic, clinical, and outcome variables. These variables will be summarized across treatment groups as well as strata of baseline antibody levels (none versus low) and compared for possible confounding of the primary and secondary comparisons. For example, what are the univariate and multivariate factors related to the initial good response to mRNA vaccination—data collected at the time of enrollment in all 1200 study subjects. Of additional interest are factors related to response to receiving the Janssen Ad26.CoV2.S vaccine as well as developing COVID infection at 2 years.

The **primary comparison (randomized trial of immunosuppression adjustment)** will focus on a chi-square test of vaccination response between those patients that did not have reduced immunosuppression versus those that did have a change in immunosuppression. Only the patients with a zero (undetectable) antibody level at the time of study enrollment will be compared.

Other analyses will focus on the overall incidence rate of reaching the primary endpoint across all patients or stratified by antibody levels (zero or low) at the time of screening. These analyses will be carried out using one-sample or two-sample chi-square tests. In addition, there is interest if possible confounding variables have any impact on reaching the primary endpoint. These analyses will focus on univariate and multivariate logistic regression models of binary response based on possible confounding variables.

Studying the durability of antibody production will utilize longitudinal analyses such mixed effects models to account for multiple (correlated) observations from the same individual. Assumptions of these models will be assessed through the residual plots.

Finally, we are interested in assessing changes in infection rate and cause-specific mortality during follow-up. We will analyze time to infection or COVID-related death using standard survival analysis procedures such as Kaplan-Meier estimation and Cox regression.

Handling of Missing Data

Queries in the Medidata Rave system will be used to identify outliers as well as missing and inconsistent data entered into the system. An example would be dates that appear out of order such as a death prior to an infection.

After data has been collected and locked as an analysis dataset, missingness will be assessed for degree as well as randomness. If the amount of missing data is small, incomplete observations will be removed from analyses of interest. On the other hand, imputation using chained equations (MICE) or random forests may be applied in the case of observations that are missing at random.

Multiplicity

There will be only a single analysis of the primary outcome across two treatment groups and therefore multiplicity is not a concern. However, for comparisons of possible confounding variables across treatment groups, multiple testing may give rise to elevated type I error. For these analyses we will consider correcting the p-values via the Benjamini-Hochberg or other methods.

Statistically significant differences on overall comparisons will be explored using multiple pairwise comparisons of each of the (n) groups using Bonferroni correction for multiple comparisons. Mean scores and standard deviation for each group will be calculated. Subsequent multiple comparisons via Tukey's procedure will be set at 0.01 to control Type I error rate.

A Note on the Incidence of COVID 19 at 2 Years

The major reason for the large numbers of patients is to have a reasonable chance of demonstrating a difference in COVID-related complications in responders vs low/non-responders after receiving the Janssen Ad26.COv2.s vaccine. The risk of COVID 19 infections in patients without anti-SARS-CoV-2 spike protein antibody is unknown and the risk of COVID infection going forward in the US also is unknown. Over the past year prior to vaccination programs, the COVID infection rate in our patient population has been approximately 10% per year with death rates of approximately 2% overall per year.

The comparisons here are one-sample comparisons of Kaplan-Meier estimates of the incidence of infection or mortality versus historical incidences of 10% and 2%, respectively.

COVID Infection Rates: Using an assumed 10% infection rate per year as the null hypothesis in the 400 patients that had an undetectable or low mRNA vaccine response, an infection rate of less than 7% will result in 90% power to demonstrate statistical significance by the one-sample log-rank test.

COVID-Related Mortality: For mortality, a reduction from an annual rate of death due to COVID of 2% in the non-responders to 0.7% in the responders would result in 80% power to demonstrate statistical significance by the one-sample log-rank test.

Interim Analysis

No formal interim hypothesis testing will be considered and therefore alpha-spending or control of type 1 error is not of concern for this study. Data summaries will be used throughout the study to audit data quality, to create reports for the regulatory requirements (i.e.. IRB, DMSB, etc.) and to ensure the overall study is running smoothly.

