This study is a phase III, prospective, open label clinical trial with one randomized arm. Its goal is to meet the unmet clinical need to provide vaccine induced immunity for our immunocompromised kidney transplant patients after receiving two or more doses of the Pfizer or Moderna COVID-19 vaccine (see Figure below for overview). Subjects will be pre-screened and interested qualified

subjects will be offered participation in this trial and, if applicable, consented. Once consented, serum levels of anti-SARS-CoV-2 spike protein antibody will be obtained. Patients with levels ≥ 250 U/ml will be followed for two years without receiving the Janssen Ad26.CoV2.S vaccine for clinical outcomes (COVID infection, graft and patient survival).

Study Schematic: Augmenting Anti-COVID Immunity In Transplant Recipients Via Heterologous Prime Booster Vaccination With Janssen Ad26.CoV2.S Vaccine

*Clinical endpoints include COVID-19 infection (primary endpoint) and secondary endpoints (hospitalization, infectious complications, patient survival, graft survival, significant AEs related to vaccine or to reduction in immunosuppression, de novo alloantibody)

** Exact cut-off still to be determined

Segment I

Patients with levels >0 but <250 U/ml of anti-SARS-CoV-2 spike protein antibody levels will receive one dose of the Janssen Ad26.CoV2.S vaccine. Their anti-SARS-CoV-2 spike protein antibody levels will be measured at multiple time points after receiving the Janssen Ad26.CoV2.S vaccine. Patients with undetectable anti-SARS-CoV-2 spike protein antibody levels (i.e. with levels = 0) will be randomized 1:1 (stratified by the number of mRNA doses received 2 vs 3) to receive the Janssen Ad26.CoV2.S vaccine and either: 1) continue on their current immunosuppression regimen or 2) have a transient immunosuppression medication adjustment prior receiving the Janssen Ad26.CoV2.S vaccine (described in Section 5.2.1).

Segment II

Patients in Segment I who received Janssen Ad26.CoV2.S vaccine while maintained on their usual immunosuppression medication dosage and did not reach the anti-SARS-CoV-2 spike protein antibody endpoint (≥ 250 U/ml) at 28 days will be offered an additional Janssen Ad26.CoV2.S vaccination. In this segment, immunosuppression will be adjusted (as described in Section 5.2.1)

and anti-SARS-CoV-2 spike protein antibody levels will be assessed at 28 days after the second vaccination with the Janssen Ad26.CoV2.S vaccine as the primary endpoint.

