5.2 Treatment Regimen

5.2.1 Immunosuppression Adjustment

Immunosuppression adjustment will occur 2 weeks prior to receiving the Janssen Ad26.COV2.S vaccine and continue for 28 days receiving the Janssen Ad26.COV2.S vaccine.

Given that transplant patients are maintained on immunosuppressive regimens that vary slightly, immunosuppression adjustment will need to be somewhat individualized to the patient. However, general rules can be implemented.

Two weeks prior to receiving the Janssen Ad26.COV2.S vaccine, patients randomized to immunosuppression adjustment (or offered immunosuppression adjustment in Segment II) will be considered individually and adjustments will be made by a nephrologist with knowledge of the patient's clinical situation. General rules for adjustment are as follows:

1. For patients receiving mycophenolate mofetil (MMF) or azathioprine (AZA), a calcineurin inhibitor (CNI) (typically tacrolimus or cyclosporine), and Prednisone. Adjustment will involve stopping MMF or AZA and starting 10 mg Prednisone/day. **Note:** most patients will be in this group.
2. For patients not on MMF, but on CNI and Prednisone, the CNI dose will be decreased by 50%,
3. For patients on belatacept, which is typically taken with MMF and Prednisone, MMF will be stopped, and belatacept and Prednisone will be modified to 10 mg a day.
4. Other patients are adjusted on a case-by-case basis by the sponsor-investigator and the co-investigators—ex. Tac-mTOR inhibitor—Reduce Tac by 50%.

28 days after receiving the Janssen Ad26.COV2.S vaccine, study subjects in this arm will resume their prior doses of immunosuppression and will be followed as per protocol and as clinically indicated by the transplant team.

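### Baseline tests between the randomized arms cannot show confounding, and the valid but unadjusted primary chi-square leaves a little efficiency unused

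*Combined protocol and SAP*

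**What the plan says.** Section 6.8 (Statistical Methods) summarizes baseline, clinical and outcome variables across treatment groups and across antibody strata (none versus low). They are then "compared for possible confounding of the primary and secondary comparisons". The Multiplicity paragraph of the same section recognizes that testing such variables across treatment groups can inflate type I error, and adds: "For these analyses we will consider correcting the p-values via the Benjamini-Hochberg or other methods".

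The primary comparison in section 6.8, and in the Study Summary, is a chi-square test of response by randomized arm among patients with undetectable antibody. It names no covariate and no stratum. The randomization itself is "stratified by the number of mRNA doses received 2 vs 3" (section 3, Segment I; also section 3.1.1). Logistic models of response on possible confounders are planned in section 6.8, but under other analyses. No covariates are listed, and nothing says that the models contain the arm.

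Section 5.2.1 states that "immunosuppression adjustment will need to be somewhat individualized to the patient" and gives four rules that depend on the drugs a patient takes at baseline. Regimen is not a randomization stratum. Section 6.7 sets the test conditions: "All tests will be carried out using two-side hypothesis tests with a significance level of 0.05 unless otherwise noted".

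**The concern.** A significance test of a baseline variable between randomized arms tests a null hypothesis that randomization has already made true. A small p-value does not identify a confounder, and a large one does not show that an imbalance is harmless. What matters for the analysis is how strongly the variable predicts response, and that is judged before the data are seen.

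The primary test also leaves out information the trial already has. The dose-number stratum was thought important enough to balance by design. Section 1.5.9 names maintenance immunosuppression as one of the likeliest reasons for poor antibody response. Medical history, demographics and immunosuppression are recorded at screening (section 6.1.1), as is mRNA vaccine history (section 5.6). At stake are some power, a test that is slightly conservative if the strata are prognostic, and an adjusted estimate of the arm effect that the plan does not define.

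**Working it through.** **1. Inputs from the documents.** 150 per arm, two-sided alpha 0.05, 20% versus 37% as the worked example, and 20% versus 60% as the expected rates (section 6.7). On the scale: "Effect sizes are based on the square-root arcsine transformation". The documents give no prognostic strengths, no split between 2 and 3 doses, and no regimen shares beyond saying that most patients fall under the first rule. These are assumed below.

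**2. The plan's own figures.** With h = |2·asin√p₁ − 2·asin√p₂| and power = Φ(h·√(n/2) − 1.960):

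- 20% vs 37%: h = 1.3078 − 0.9273 = 0.3805; 0.3805 × √75 = 3.295; Φ(3.295 − 1.960) = Φ(1.335) = 0.909. The plan says that "a true response rate of 37% in the patients in the altered immunosuppression group will reject the null hypothesis" with 90% power. Reproduced.
- 20% vs 60%: h = 1.7722 − 0.9273 = 0.8449; n = 2 × ((1.960 + 1.282)/0.8449)² = 29.4, so 30. The plan says "30 patients would be required for each arm to achieve 90% power". Reproduced.
- The other rows stated as 0.9 give 0.891 to 0.912.

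The stated power is right and is not in dispute.

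**3. What baseline tests would show.** Under sound randomization, k independent tests at 0.05 give at least one significant difference with probability 1 − 0.95^k: 40% for k = 10 and 64% for k = 20.

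**4. Size of chance imbalance in regimen.** If a share q lies outside the main regimen, the SD of the arm difference is √(2q(1 − q)/150). For q = 0.10 this is 0.035, a 95% range of ±7 percentage points. For q = 0.30 it is 0.053, a range of ±10 points.

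**5. Stratified test (CMH) against the unadjusted test.** Simulation with 8,000 trials per cell and 300 patients. Assumptions: half with 2 and half with 3 doses, arms balanced within dose stratum, 80% in the main regimen, 20% overall control response, and 37% in the other arm for power.

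| Assumed OR, dose / regimen | Type I error: unadjusted | by dose | by dose × regimen | Power: unadjusted | by dose | by dose × regimen |
|---|---|---|---|---|---|---|
| 1 / 1 | 5.1% | 5.1% | 5.0% | 91.1% | 91.1% | 91.0% |
| 3 / 2 | 4.8% | 5.1% | 5.3% | 91.7% | 92.6% | 92.5% |
| 5 / 3 | 4.1% | 4.9% | 5.0% | 92.4% | 93.6% | 94.2% |
| 10 / 5 | 3.4% | 4.8% | 4.7% | 93.1% | 95.4% | 96.6% |

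The change in power for dose × regimen is −0.1, 0.8, 1.8 and 3.5 points. The unadjusted test never exceeds its level beyond simulation error. It becomes conservative as the strata become more prognostic.

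**6. Logistic model against chi-square.** Simulation with 3,000 trials per setting, 150 per arm, 20% vs 37%, one binary covariate (75% prevalence) and two continuous covariates.

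| Assumed OR, binary / per SD | Chi-square | Adjusted | Change |
|---|---|---|---|
| none | 90.1% | 89.7% | −0.4 |
| 2 / 1.3 | 91.4% | 91.9% | +0.5 |
| 3 / 1.5 | 91.5% | 93.2% | +1.7 |
| 4 / 1.8 | 91.3% | 95.0% | +3.7 |

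The Monte Carlo standard error of one power estimate is √(0.914 × 0.086/3000), about 0.5 points, so the −0.4 and +0.5 are small against simulation noise. Adjusted type I error was 4.55% to 5.45% (2,000 null trials per setting at 28% response).

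**7. At the expected rates.** For 20% vs 60% with 150 per arm, 0.8449 × √75 − 1.960 = 5.36, so power is already 1.00 and adjustment can add nothing of note.

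**The case against.** The strongest case for leaving the plan alone has four parts.

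- **The primary test is pre-specified.** A reader might infer that baseline p-values will decide, after the data are seen in an open-label trial, whether the primary result is adjusted. The documents do not say this. Section 6.8 fixes the chi-square and states that the primary outcome is analysed once, and no passage lets a baseline finding change that. This stands in full.
- **The chi-square is valid.** A reader might infer that a chance imbalance in regimen or age biases the primary estimate. It does not: chance imbalance is already covered by the test's type I error, which stayed at about 5% or below in step 5. This also stands.
- **The text is softer and broader than it may look.** P-value correction is only to be considered. The comparison sentence also covers antibody strata, and its example concerns response to mRNA vaccination in all 1,200 subjects. Section 5.3 forms groups partly by antibody result. Confounder checks are legitimate for those non-randomized contrasts. This stands, but the wording does not exclude the two randomized arms, and there the tests serve no purpose.
- **Covariate models are already planned.** They are, so the gap is one of specification, not absence. Without a covariate list or an arm term they do not define an adjusted arm effect.

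A reader might also infer that, because baseline regimen determines which adjustment a patient receives, a regimen term would repair the comparison. That argument concerns effect heterogeneity, which a main-effect term does not address. Showing the effect by regimen class does.

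**Conclusion.** The point holds as a minor, optional improvement. Significance tests of baseline variables between the randomized arms are uninformative. The primary chi-square is valid and pre-specified, but it leaves out the randomization stratum and prognostic data already collected. The cost is efficiency: roughly 0 to 4 power points at 20% vs 37%, a conservative test (3.4% in the most extreme scenario) when the strata are prognostic, and next to nothing at 20% vs 60%. If the covariates are not prognostic, adjustment loses about 0.4 points.

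These sizes rest on assumed odds ratios, dose split and regimen shares, none of which the documents give. The statement that differences are due to chance applies to all randomized patients. The primary analysis uses the all-completed population (section 6.9), where exclusions after randomization could create real differences. That is a separate matter, and baseline p-values would not repair it.

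**What to change.** 1. In section 6.8, present baseline variables by randomized arm descriptively, without significance tests. Keep confounder checks, with any p-value correction, for the non-randomized contrasts, and say which contrasts are meant.
2. Pre-specify the primary analysis as a logistic model, or a CMH test, with arm, number of mRNA doses (2 vs 3, using the levels applied at randomization) and baseline regimen class. In the logistic model add age, time since transplant and time since last mRNA dose.
3. Define the regimen classes before analysis and collapse sparse ones in advance. Section 5.2.1 describes its first group as taking prednisone, while section 1.5.9 says prednisone is used only sometimes. These passages must be reconciled so that every patient belongs to one class.
4. Report the standardized risk difference with 95% confidence interval, keep the chi-square as supportive, and show the arm effect by regimen class descriptively.

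Cost: SAP wording, a covariate and class definition, and one model. No new data are needed. The downside is a trivial power loss if the covariates turn out not to be prognostic.
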